6.1 Number of subjects

Number of subjects planned to be randomised: 282

6.2 Inclusion criteria

For an eligible subject, all inclusion criteria must be answered “yes”.

1. Informed consent obtained before any trial-related activities. Trial-related activities are any procedures that are carried out as part of the trial, including activities to determine suitability for the trial
2. BMI ≥ 30 kg/m²
3. Maximum 5 kg self-reported weight change within the past 90 days since screening
4. Age ≥ 18 years at the time of signing informed consent
5. Increased physical activity is considered to be safe as judged by the investigator

6.3 Exclusion criteria

For an eligible subject, all exclusion criteria must be answered “no”.

1. HbA_{1c} $\geq 6.5\%$ (at screening visit), or diagnosis of type 1 or type 2 diabetes mellitus
2. Recent history of cardiovascular disease (myocardial infarction or stroke within the past 6 months), severe congestive heart failure (NYHA class III, IV), or second degree or greater heart block
3. Hypersensitivity to liraglutide or any product components
4. Personal or family history of Medullary Thyroid Carcinoma (MTC), or Multiple Endocrine Neoplasia type 2 (MEN2)
5. Female who is pregnant, breast-feeding or intends to become pregnant or is of child-bearing potential and not using an adequate contraceptive method (adequate contraceptive measure as required by local regulation or practice)
6. Uncontrolled thyroid disease, defined as TSH > 6 mIU/L or < 0.4 mIU/L (at screening visit)
7. Use in past 90 days since screening of medications known to induce significant weight loss (e.g., prescription weight loss medications) or weight gain (e.g., chronic use of oral steroids, second generation antipsychotics)
8. History of (or plans for) weight loss surgery (e.g. bariatric, intra-gastric balloons, maestro system) or implant of weight loss device (e.g., Reshape, vBloc). However, liposuction and/or abdominoplasty performed > 1 year before screening is allowed
9. History of pancreatitis (acute or chronic)
10. History of major depressive disorder within the past 2 years since screening
11. Diagnosis of other severe psychiatric disorder (e.g., schizophrenia, bipolar disorder)

12. A Patient Health Questionnaire-9 (PHQ-9) score of ≥ 15 at screening or randomisation
13. Any lifetime history of a suicide attempt
14. Any suicidal behaviour within the past 30 days since screening
15. Any suicidal ideation of type 4 or 5 on the Columbia-Suicide Severity Rating Scale (C-SSRS) within the past 30 days at screening or randomisation
16. Inadequately treated blood pressure defined as Grade 3 hypertension or higher (Systolic ≥ 180 mmHg or diastolic ≥ 110 mmHg)
17. History of malignancy (except for non-melanoma skin cancer) within the past 5 years
18. Any disorder, not covered by any of the other exclusion criteria, which in the investigator's opinion, might jeopardise the subject's safety or compliance with the protocol
19. Known or suspected abuse of alcohol or narcotics
20. Language barrier, mental incapacity, unwillingness or inability to adequately understand or comply with study procedures
21. Subjects from the same household participating in the trial
22. Participation in any clinical trial with or without an investigational medicinal product within the past 90 days before screening
23. Previous participation in this trial. Participation is defined as signed informed consent

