1. Informed consent obtained before any trial-related activities. Trial-related activities are any procedures that are carried out as part of the trial, including activities to determine suitability for the trial
2. BMI ≥ 30 kg/m²
3. Male or female, age ≥ 18 years at the time of signing informed consent

Key exclusion criteria

1. HbA_{1c} $\geq 6.5\%$ (at screening visit), or diagnosis of type 1 or type 2 diabetes mellitus
2. Recent history of cardiovascular disease (myocardial infarction or stroke within the past 6 months), severe congestive heart failure (NYHA class III, IV), or second degree or greater heart block
3. Personal or family history of Medullary Thyroid Carcinoma (MTC), or Multiple Endocrine Neoplasia type 2 (MEN2)
4. Female who is pregnant, breast-feeding or intends to become pregnant or is of child-bearing potential and not using an adequate contraceptive method (adequate contraceptive measure as required by local regulation or practice)
5. Use in past 90 days of medications known to induce significant weight loss (e.g., prescription weight loss medications) or weight gain (e.g., chronic use of oral steroids, second generation antipsychotics)
6. History of pancreatitis (acute or chronic)
7. History of major depressive disorder within the past 2 years
8. Any lifetime history of a suicide attempt
9. Inadequately treated blood pressure defined as Grade 3 hypertension or higher (Systolic ≥ 180 mmHg or diastolic ≥ 110 mmHg)
10. History of malignancy (except for non-melanoma skin cancer) within the past 5 years

Assessments:

Efficacy

- Body measurement (weight and waist circumference)
- Blood pressure
- Six minutes walking distance (m)
- Clinical outcome assessments (IWQoL-Lite for CT, Short Form 36 v2.0 acute)

Safety

- Adverse events
- Resting pulse
- ECG
- Biochemistry and haematology

Trial products:

The following products will be delivered by Novo Nordisk A/S Denmark:

- Liraglutide 6 mg/mL, solution for injection, 3.0 ml PDS290 pen-injector
- Liraglutide placebo, solution for injection, 3.0 ml PDS290 pen-injector

¹Counselling is the intensive behaviour therapy (CMS-IBT)

²PGI-S and PGI-C questions are different for the WRSS and 6MWT

³For women of childbearing potential: A negative pregnancy test (s-HCG) is required for inclusion

⁴Breast neoplasm follow up form is to be filled up only for female subjects

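### Exclusion 14 ties suicidal behaviour to screening only, so new non-attempt behaviour before randomisation need not exclude a subject

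*Protocol*

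**What the plan says.** Four consecutive exclusions in Protocol Section 6.3 cover depression score and suicidality:

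- **12:** PHQ-9 of 15 or more, at screening or at randomisation.
- **13:** a suicide attempt at any time in life, with no date limit.
- **14:** "14. Any suicidal behaviour within the past 30 days since screening".
- **15:** type 4 or 5 ideation on the C-SSRS, "within the past 30 days at screening or randomisation".

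Section 8.4.7 describes the C-SSRS as covering behaviour as well as ideation, but names only type 4 or 5 ideation as a reason to exclude. The single randomisation criterion in Section 6.4 concerns the food diary. Amendment 1 leaves Section 6.3 unchanged.

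**The concern.** Before first dose, mandatory rules check the depression score and serious ideation a second time. Suicidal behaviour has no clear second check, and the protocol gives no reason for the difference. The same instrument assesses both behaviour and ideation.

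Two things are at stake. A subject with new suicidal behaviour during the run-in could be eligible as written. Sites could also apply the criterion differently. The reading matters after randomisation too: Section 6.5, criterion 1, makes stopping trial product compulsory for anyone included in breach of an exclusion criterion. How criterion 14 is read therefore decides whether that rule applies when interval behaviour comes to light later.

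**Working it through.** No arithmetic applies beyond a count. The question is what the wording covers.

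**1. Time anchors in Sections 6.2 and 6.3**

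| Form of anchor | Criteria | Count |
|---|---|---|
| past … since screening | inclusion 3; exclusions 7, 10, 14 | 4 |
| before screening | exclusions 8, 22 | 2 |
| at screening or randomisation | exclusions 12, 15 | 2 |
| at the screening visit | exclusions 1 (HbA1c part), 6 | 2 |
| past period, no anchor visit stated | exclusions 2, 17 | 2 |

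Within the block 12 to 15, two criteria name randomisation, one has no date limit, and only 14 is tied to screening alone.

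**2. Which way the window in criterion 14 runs**

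- *Look-back from screening (likelier).* The same form appears where only history makes sense: "Maximum 5 kg self-reported weight change within the past 90 days since screening" and "History of major depressive disorder within the past 2 years since screening". The Section 1 summary restates exclusion 7 as a plain look-back: "Use in past 90 days of medications known to induce significant weight loss".
- *Forward from screening (cannot be ruled out).* Where the protocol clearly means a backward window it can say so: "liposuction and/or abdominoplasty performed > 1 year before screening is allowed" in exclusion 8 and "within the past 90 days before screening" in exclusion 22. Read literally, this version covers the run-in but leaves behaviour before screening uncovered.

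The first reading leaves the run-in open. The second leaves the period before screening open.

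**3. What else could catch the subject on the look-back reading**

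| Provision | Catches new non-attempt behaviour? |
|---|---|
| Exclusion 11 | only with another severe psychiatric diagnosis |
| Exclusion 12 | only if PHQ-9 is 15 or more |
| Exclusion 13 | no, attempts only |
| Exclusion 15 | only with type 4 or 5 ideation in the past 30 days |
| Exclusion 18 | only at the investigator's discretion, and worded for a disorder |
| Section 6.4 | no, food diary only |

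**4. Length of the interval**

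Section 6.4 requires at least 5 diary days between screening and randomisation, and the heading of Section 8.2.9 refers to a 7-day diary. The maximum is set in the flow chart (Section 2), which was not in the text available for this review.

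**The case against.** The strongest case against is that this is a wording preference with almost no residual gap.

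- **All exclusions must be answered no before a subject is eligible, so an investigator can treat 14 as still open at randomisation.** That is possible, but asking the question again does not move a window anchored to screening.
- **Screening-only anchors are common in this protocol.** This is true. On the look-back reading, inclusion 3 and exclusions 1 (HbA1c part), 6, 7 and 10 share the feature, and 12 and 15 are the exceptions. The comparison that matters is still with 12 and 15, because they show that the protocol meant to re-check this risk before dosing. Exclusion 10 (major depressive disorder) has the same anchor, but the PHQ-9 re-check partly covers it.
- **The uncovered case is very small.** This stands. The protocol does not define where suicidal behaviour ends and an attempt begins, so the size of the gap also depends on the C-SSRS itself.
- **The subject would not be unmanaged.** This also stands. Adverse events are collected from the first trial-related activity after consent (Section 12.2). Section 8.8.5 calls for treatment, careful monitoring and referral to a mental health professional for any suicidal behaviour. If the subject refuses referral, the investigator must record whether staying in the trial is safe. Section 6.5 allows trial product to be stopped for a safety concern. It makes stopping compulsory where the investigator judges there is a safety concern (criterion 2), or for a psychiatric disorder that treatment cannot adequately control (criterion 10). All of these are management or judgement, and the stopping rules act after randomisation. None makes the subject ineligible.

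**Conclusion.** The concern holds as a minor patient-safety point. On the likelier reading of criterion 14, no mandatory exclusion need cover non-attempt suicidal behaviour that begins between screening and randomisation. On the other reading the criterion is ambiguous and misses behaviour before screening.

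The gap requires all of the following: behaviour short of an attempt, PHQ-9 below 15, no type 4 or 5 ideation in the past 30 days, no other exclusion met, and an investigator who does not invoke exclusion 18. The documents give no event rate, so no probability is offered. Primary and secondary endpoints, sample size and analysis are unaffected.

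Confidence is medium, because the conclusion rests on the look-back reading and the flow chart could not be checked.

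**What to change.** Make two wording changes:

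1. In Section 6.3, have criterion 14 exclude any suicidal behaviour "within the past 30 days at screening or randomisation", the anchor criterion 15 already uses.
2. In the last sentence of Section 8.4.7, name suicidal behaviour alongside type 4 or 5 ideation as exclusionary over the same period and at the same two visits.

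No assessment appears to be added. The C-SSRS already assesses behaviour, and criterion 15 together with Section 8.4.7 implies that it is given at randomisation. That is an inference to confirm against the flow chart.

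For an approved protocol this is a minor amendment that needs approval or a favourable opinion before use (Section 25). The only other cost is, at most, a rare extra exclusion. Planned recruitment was 10 weeks (Section 7), so if enrolment has closed, the change belongs in the sponsor's eligibility template for later protocols.

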6.4 Randomisation criterion

1. Have kept a food diary for at least 5 days (minimum one entry per day) in the period between screening and randomisation

To be randomised, the above randomisation criterion must be answered "yes".

6.5 Criteria for premature discontinuation of trial product

Efforts must be made so that subjects attend and complete all scheduled visit procedures. Subjects should stay in the trial regardless of adherence to randomised treatment, visit schedule or missing assessments. Only subjects who decline any further contact with the site in relation to the trial or withdraw consent are considered as withdrawn from the trial (see Section [6.6](#)).

The subject may be prematurely discontinued from trial product at the discretion of the investigator due to a safety concern.

The subject must be prematurely discontinued from trial product if the following applies:

1. Included in the trial in violation of any of the inclusion and/or exclusion criteria and/or randomisation criteria
2. Safety concern (not covered by any of below criteria) or unacceptable intolerability to trial product, as judged by the investigator

3. Hypersensitivity to trial product(s). If a hypersensitivity reaction occurs, discontinue trial product and other suspect medications and promptly seek medical advice
4. Pregnancy
5. Intention of becoming pregnant
6. Suspicion of pancreatitis (see Section [8.4.2.2](#) and [8.8.1](#))
7. Suspicion of acute gallstone disease (see Section [8.4.2.2](#) and [8.8.2](#))
8. Suspicion of drug-induced liver injury (DILI) (see Section [8.4.2.2](#) and [8.8.4](#))
9. Calcitonin ≥ 100 ng/L
10. Psychiatric disorder(s) that cannot be adequately treated with psycho- and/or pharmacotherapy (see Section [8.4.2.2](#), [8.8.5](#) and [8.6.4](#)).
11. Initiation of anti-obesity medication and/or (plans for) weight loss surgery
12. Initiation of treatment with glucagon-like peptide-1 receptor agonist (GLP-1 RA)
13. Simultaneous participation in another clinical trial of an approved or non-approved investigational medicinal product

See Section [8.1](#) for procedures to be performed for subjects discontinuing trial product prematurely.

It is allowed for subjects meeting the premature discontinuation criteria or who have wished to discontinue prematurely to be restarted on the trial product should the suspicion not be confirmed or if the condition has been resolved at the investigator's discretion. Trial product may be restarted for subjects meeting discontinuation criteria 7 should the gallbladder be removed.

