5.3 Treatment of subjects

5.3.1 Investigational medicinal product

The investigational medicinal product (IMP) is injected subcutaneously (s.c.) once daily for 56 weeks. Dose escalation of trial product will take place during the first 4 weeks after randomisation (see [Table 5–1](#)).

Table 5–1 Dose Escalation and treatment period

| IMP | Dose | Duration |
|---------------------|--------|----------|
| Liraglutide/placebo | 0.6 mg | 1 week |
| Liraglutide/placebo | 1.2 mg | 1 week |
| Liraglutide/placebo | 1.8 mg | 1 week |
| Liraglutide/placebo | 2.4 mg | 1 week |
| Liraglutide/placebo | 3.0 mg | 52 weeks |
| Follow up period | 0 mg | 4 weeks |

If the subject does not tolerate an increased dose during the dose escalation window, the investigator can delay the dose escalation by maintaining the subject at the current dosage step for one additional week. Such a delay is allowed only once during dose escalation (i.e. maximum allowed time for complete dose escalation to 3.0 mg is 5 weeks). After reaching the maintenance dose (3.0 mg), the dose and dosing frequency should not be changed.

If a single dose is missed, once-daily regimen should be resumed as prescribed at the next scheduled dose. If more than 3 consecutive days have elapsed since the last dose, subject should re-initiate dose escalation, (i.e., restart the dosing at 0.6 mg and follow the dose escalation schedule again). This is done to reduce the occurrence of gastrointestinal symptoms associated with re-initiation of treatment.

NB: Additional or increased dose should not be taken to make up for missed doses.

Trial product can be taken at any time of day, irrespective of timing of meals. Trial product can be injected subcutaneously in the abdomen, thigh, or upper arm. The injection site and timing can be changed without dose adjustment.

NB: Trial product must not be administered intravenously or intramuscularly.

If a subject cannot tolerate the 3.0 mg dose, or if any of the other treatment discontinuation criteria are met, then treatment with trial product must be discontinued. For treatment discontinuation reasons, please refer to Section [6.5](#). In case this happens, it is acceptable to restart trial product (at the discretion of investigator and according to the local clinical practice); the dose must be escalated according to the algorithm above, and date of restart and rationale must be documented in the CRF.

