If a subject meets a discontinuation criterion, the trial product must be immediately discontinued and the date should be noted in the medical records and eCRF. Discontinuation can be either temporary or permanent. The last paragraph of Section [6.5](#) outlines which discontinuation can be considered temporary. The investigator must note down the date in the medical record and the eCRF once there is resolution and the subject has re-started the trial product.

The subject may also wish to discontinue trial product temporarily or permanently, irrespective meeting any criteria. Discontinuation of treatment with trial product, whether temporary or permanent, must not prompt the investigator to withdraw the subject from the trial. Instead, the subject should maintain adherence to trial visits (including CMS-IBT) and procedures to the extent possible.

In cases where the subject is not willing to attend all scheduled visits after discontinuation of trial product, efforts must be made to collect as much of the scheduled data as possible. Especially important is collection of the data points (primarily body weight) at visit 24 (week 56). Statistical considerations emphasizing the importance can be found in Section [17](#).

Premature trial product discontinuation should be registered in the eCRF and in IWRS. The trial product can be interrupted by performing a 'treatment status' session in IWRS, to indicate subject should no longer receive trial product. The primary reason for discontinuation of trial product must be specified when recording the treatment discontinuation in the eCRF. If the discontinuation of trial product is judged permanent or of a longer period, drug accountability until discontinuation must be performed in IWRS.

If the subject has previously discontinued trial product, it is possible, at the discretion of the investigator and at the wish of the subject, to re-initiate treatment with trial product. This will only apply, if it can be confirmed that the subject has not withdrawn consent, and does not fulfil any of the criteria leading to permanent discontinuation or if a criterion leading to temporary discontinuation has been resolved. A 'treatment status' session is performed in the IWRS, to indicate that the subject should again receive trial product. See Section [10](#) for registration in IWRS. This should be further noted in the medical records and eCRF.

Withdrawal from trial

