In case of suspicion of DILI, following additional information should be reported if available on the drug induced liver injury form:

- Signs and symptoms of drug induced liver injury
- Specific laboratory test supporting a diagnosis of drug induced liver injury (see Section [8.8.3](#))
- Treatment given for the event
- Relevant risk factors associated with the event

Prompt testing (at central laboratory) including alanine aminotransaminase (ALT), aspartate aminotransferase (AST), alkaline phosphatase (ALP), international normalised ratio (INR) and total bilirubin (TBL) should be done and trial product should be discontinued until the abnormalities return to normal or baseline state.

Additional clinical information such as related symptoms, risk factors and contributing conditions (e.g., viral hepatitis, autoimmune hepatitis, alcoholic hepatitis, hepatobiliary or pancreatic disorders) should be gathered to seek a possible cause of the observed laboratory test abnormalities.

The event should be reported as an AE requiring additional data collection (see Section [12.1.5](#)).

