8.8 Additional safety assessments

8.8.1 Suspicion of acute pancreatitis

If pancreatitis is suspected, trial product should promptly be discontinued (no 'treatment status' session should be made in IWRS before diagnosis of acute pancreatitis is confirmed) and appropriate management should be initiated. Appropriate additional examinations must be performed, including local measurement of amylase and lipase.

The event should be reported as an AE requiring additional data collection (see Section [8.4.2.2](#) and Section [12](#)).

The diagnosis of acute pancreatitis requires two of the following three features:

- Abdominal pain consistent with acute pancreatitis (acute onset of a persistent, severe, epigastric pain often radiating to the back)
- Serum lipase activity (and/or amylase activity) at least three times greater than the upper limit of normal
- Characteristic findings of acute pancreatitis on imaging (CT/MRI).

Abdominal pain

Most patients with acute pancreatitis experience abdominal pain that is located generally in the epigastrium and radiates to the back. The onset of the pain may be swift reaching maximum intensity within 30 minutes; it is frequently unbearable and characteristically persists for more than

24 hours without relief. The pain is often associated with nausea and vomiting. Physical examination usually reveals severe upper abdominal tenderness at times associated with guarding.

Lipase and amylase

In general, both amylase and lipase are elevated during the course of acute pancreatitis. The serum lipase may remain elevated slightly longer than amylase. The level of the serum amylase and/or lipase does not correlate with the severity of acute pancreatitis. In general, serum lipase is thought to be more sensitive and specific than serum amylase in the diagnosis of acute pancreatitis.

If acute pancreatitis is confirmed, the subject must be permanently discontinued from trial product and appropriate treatment and careful monitoring of the subject should be initiated. Furthermore, the subject should still remain in the trial (see Section [8.1](#)).

If acute pancreatitis is ruled out, trial product should be re-initiated at the investigator's discretion.

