8.8.4 Hepatic event (suspicion of drug-induced liver injury)

Please consider discontinuing trial product if :

- 1) ALT or AST >5xUNL, or
- 2) ALT or AST > 3x UNL and (total bilirubin >2xUNL or INR >1.5), or
- 3) ALT or AST >3xUNL with the appearance of fatigue, nausea, vomiting, right upper quadrant pain or tenderness, fever, rash, and/or eosinophilia (>5%).

For the above events, prompt repeat testing at central laboratory, of ALT, AST, ALP, INR and total bilirubin should be done. Thereafter, repeat testing (at central laboratory) of ALT, AST, ALP, INR and total bilirubin should be done regularly until the abnormalities return to normal or baseline state. Additional clinical information such as related symptoms, risk factors and contributing conditions (e.g. viral hepatitis, autoimmune hepatitis, alcoholic hepatitis, hepatobiliary or pancreatic disorders) should be gathered to seek a possible cause of the observed laboratory test abnormalities. Although the trial product is discontinued, no ‘treatment status’ session should be made in IWRS and the subject should remain in the trial.

The event should be reported as an AE requiring additional data collection (see Section [8.4.2.2](#) and Section [12](#)).

If DILI is confirmed, the subject should permanently discontinue the trial product. Appropriate treatment and careful monitoring of the subject should be initiated. However, the subject should remain in the trial (see Section [8.1](#)).

Trial product can be re-initiated at the investigator’s discretion, if diagnosis of DILI is not supported.

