Based on a limited number of reports in the clinical development programme for liraglutide 3.0 mg, a numerical imbalance was observed for events of breast neoplasms in females and colorectal adenomas in males. There were too few cases to determine whether these cases were related to liraglutide. In addition, there are insufficient data to determine whether liraglutide has an effect on pre-existing breast neoplasia. Two positively adjudicated cases of malignant colorectal carcinoma were reported in liraglutide-treated subjects and none in placebo-treated subjects.

Heart rate increase

In the clinical development programme, mean increase in resting heart rate (by 2-3 beats per minute) as well as a slight decrease in systolic blood pressure has been observed. The long-term clinical effects of the increase in resting heart rate have not been established. There is no indication that the effect on resting heart rate is dose dependent and the increase in heart rate disappears upon treatment discontinuation. When initiating treatment with liraglutide 3.0 mg, heart rate should be monitored at regular intervals consistent with usual clinical practice.

Allergic reactions

As in the case with all protein-based pharmaceuticals, treatment with liraglutide may evoke allergic reactions. These may include urticaria, rash, pruritus as well as anaphylactic reactions. As a precaution, subjects with known or suspected hypersensitivity to trial product(s) or related products will not be enrolled in the trial. In addition, subjects will be instructed to contact the site staff as soon as possible for further guidance if suspicion of a hypersensitivity reaction occurs

Pancreatitis

An association between the use of GLP-1RAs and pancreatitis has been suggested based on case reports received in clinical trials and during the post-marketing experience with liraglutide (in T2DM) and other GLP-1RAs. Few events of pancreatitis have been reported in clinical trials with liraglutide in weight management. After initiation of liraglutide 3.0 mg, subjects must be observed carefully for signs and symptoms of pancreatitis (see Section [8.8.1](#)). If pancreatitis is suspected, liraglutide 3.0 mg should promptly be discontinued and appropriate management should be initiated. If pancreatitis is confirmed, liraglutide 3.0 mg should not be restarted. Subjects with a history of pancreatitis are excluded from participation in the trial.

Acute gallstone disease

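### For a confirmed pancreatitis, gallstone or liver-injury event that later resolves, the protocol gives opposite restart instructions and does not say which prevails

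*Protocol*

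**What the plan says.** **Texts that permit restart.** Section 6.5 lists 13 criteria for mandatory stopping of trial product. Criteria 6, 7 and 8 are suspicion of pancreatitis, of acute gallstone disease and of drug-induced liver injury (DILI). Its last paragraph then opens: "It is allowed for subjects meeting the premature discontinuation criteria or who have wished to discontinue prematurely to be restarted on the trial product", on condition that this happens "should the suspicion not be confirmed or if the condition has been resolved", at the investigator's discretion. A further sentence allows restart under criterion 7 after gallbladder removal. Section 8.1 says that this paragraph "outlines which discontinuation can be considered temporary". Section 5.3.1, after covering intolerance of the full dose and the other discontinuation criteria, adds: "In case this happens, it is acceptable to restart trial product". That is subject to investigator discretion and local practice, with re-escalation, and no confirmation or resolution condition is given.

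**Texts that make the stop permanent.** Section 8.8.1: "If acute pancreatitis is confirmed, the subject must be permanently discontinued from trial product". Section 18.1: "If pancreatitis is confirmed, liraglutide 3.0 mg should not be restarted". Section 8.8.4: "If DILI is confirmed, the subject should permanently discontinue the trial product". Section 8.8.2 also makes confirmed acute gallstone disease permanent, but its closing sentence allows restart if cholelithiasis is ruled out or the gallbladder has been removed.

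**Related wording.** Section 8.4.2.2 says of suspected DILI that "trial product should be discontinued until the abnormalities return to normal or baseline state". Section 8.1 withholds re-initiation from subjects who meet a criterion for permanent discontinuation, without listing such criteria. Section 10 allows re-initiation only when no discontinuation criterion is met, and refers to Section 8.1.

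**The concern.** The two conditions in Section 6.5 are joined by *or*. The second, resolution, is met by an event that was confirmed and has since settled. That is the situation in which Section 8.8 says the stop is permanent. A site that starts at Section 8.1 and follows its pointer to Section 6.5 may restart such a subject; a site that starts at Section 8.8.1 may not. The first stake is subject safety: possible re-exposure to trial product after an event for which another section bars it. The second is consistency of the data, because Table 17-1 of the protocol (Table 2-1 of the SAP) groups subjects who stop and restart with those who never stopped.

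**Working it through.** No arithmetic decides this point, so the passages are set side by side by the subject's state. Section 5.3.1 permits restart in every row.

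| State of the subject | Section 6.5, last paragraph | Specific section | Agreement |
|---|---|---|---|
| Suspicion under criterion 6, 7 or 8, not confirmed | Restart allowed | 8.8.1, 8.8.2, 8.8.4: restart at discretion | Yes |
| Pancreatitis confirmed, then resolved | Restart allowed | 8.8.1: permanent; 18.1: no restart | No |
| DILI confirmed, then resolved | Restart allowed | 8.8.4: permanent | No |
| Gallstone disease confirmed, resolved, gallbladder in place | Restart allowed | 8.8.2: permanent; resolution is not among its restart conditions | No |
| Gallstone disease confirmed, gallbladder removed | Restart allowed | 8.8.2: one paragraph says permanent, the last allows restart | 6.5 agrees with the last sentence of 8.8.2, which conflicts with its own earlier paragraph |

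The contradiction therefore lies only in the resolution condition, and only for confirmed events under criteria 6 to 8.

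**Is precedence stated?**
1. Section 8.1 sends the question of temporary or permanent to Section 6.5.
2. Section 8.1 also excludes criteria for permanent discontinuation, but neither it nor Section 6.5 lists them. The same sentence goes on to allow restart once a temporary criterion has resolved, which leads back to Section 6.5.
3. Section 19.2 and Section 10 both refer to Section 8.1.
4. Criteria 6 to 8 cite their Section 8.8 subsections, but the restart paragraph does not say that those subsections override it.

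No passage settles the matter. Amendment 1 changes Sections 1, 2, 4.2.2.1, 4.2.2.2, 8.5.2, 17.1 and 17.4.2, so the text above is current.

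**Where the data could be touched** (SAP Sections 2.3.2.2 and 2.3.3). A restarted subject on drug at week 56 is AT or MT (week 56 value available or missing, on treatment); a permanent stop is AD or MD (available or missing, drop-out).
- *Primary jump-to-reference analysis:* uses AT and AD values alike and imputes MT and MD alike from placebo AT+AD. The label has no effect.
- *Efficacy MMRM:* uses data up to the first discontinuation, temporary or permanent, and not the week 56 label. A later restart does not enter, unless the whole pause is shorter than the SAP's eight consecutive days.
- *Multiple imputation from retrieved drop-outs, and weighted ANCOVA:* MD is represented by AD, and MT by AT. The label matters.
- *Single imputation with 0.3 kg/month regain, and tipping point:* MD and MT are imputed by different rules, at least in the liraglutide arm. The label matters if the week 56 weight is missing.

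**The case against.** The best defence is that the protocol can be read coherently. Criteria 6 to 8 are worded as suspicions and each points to Section 8.8, so the non-confirmation condition could be meant for them and the resolution condition for the others. The separate gallbladder sentence in Section 6.5 would be largely redundant if resolution already covered confirmed gallstone disease. Section 6.5 is also permissive where Section 8.8.1 is mandatory, so a site that never restarts complies with both. And although there is no consolidated list of permanent criteria, Sections 8.8.1, 8.8.2 and 8.8.4 each use the word permanent.

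This reading is possible, and a careful site may adopt it. But it is nowhere stated, and the explicit pointer in Section 8.1 runs to the paragraph that excepts nothing.

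Other parts of the defence do stand:
- Section 8.4.2.2 concerns suspected DILI and Section 8.8.4 confirmed DILI. They are different states, so this is loose wording rather than a direct contradiction.
- Section 10 is in the present tense and defers to Section 8.1. A resolved criterion is arguably no longer met.
- A reader might infer that every subject who stops is handled under conflicting rules, about 85 at the planning rate (0.30 × 282 = 84.6). The documents do not support this. The 30% is an all-cause planning ceiling, and most stops meet no opposing text.
- A reader might also infer that all 13 criteria are in conflict. The Section 6.5 wording does reach all of them, but the opposing permanence rules identified here concern only criteria 6, 7 and 8.

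**Conclusion.** The inconsistency is real and in force. It is narrow: confirmed pancreatitis or DILI that has resolved, and confirmed gallstone disease that has resolved with the gallbladder in place, together with the internal tension in Section 8.8.2. The documents give no expected count for these events, so the number affected cannot be computed. It is assumed to be small: Section 18.1 reports few pancreatitis events in weight management trials, although it notes that gallstone events were commoner on liraglutide than on placebo. The conclusion does not rest on a count, since each case is a possible re-exposure that another section bars.

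A reader might infer that the primary result is at risk through misclassification. It is not: the primary imputation does not separate the types, the effectiveness estimand applies regardless of adherence, and the label plays no part in the efficacy MMRM. The labelling effect is confined to the four sensitivity analyses named above, and to few subjects. The case for correction is mainly one of subject safety and uniform conduct across sites.

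**What to change.** Reconcile the restart text in Sections 5.3.1, 6.5 and 8.1 with Sections 8.8.1, 8.8.2, 8.8.4 and 18.1, and align the wording of Section 8.4.2.2 and Section 10. In Section 6.5 state, by cross-reference to Section 8.8 or in a short table, which criteria are permanent once confirmed, which are restart-eligible and on what condition, and which text prevails if sections differ. Section 8.1 can then cite that list when it refers to permanent criteria. The sponsor's clinical team decides which existing rule stands for each criterion; this review takes no position on that. The cost is amendment wording and a letter to sites, with no new data, procedures or analyses.
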